9.1 Monitoring of study centers

The research centers participating in the study will be monitored. For each center, at least one start visit and one closing visit must be carried out, which does not exclude the carrying out of one or more follow-up visits between these two mandatory visits.

The initial visit must be carried out before the inclusion of the first participant in that center; In it, the monitor will verify that the material to be used during the study has been received and that the personnel who will participate in the study activities have been trained on the study, as well as verify that the regulatory requirements and applicable standard operating procedures are met.

At the follow-up visit(s), the monitor will conduct a review of the study documents to confirm that: the research protocol has been followed, the applicable standard operating procedures have been followed, the data has been completed and timely, and that the AE reports have been carried out appropriately. During this visit, the monitor will discuss the findings with the researcher and define the actions that should be taken.

The closure visit will take place at the end of the study, once the last site participant has been discharged from follow-up. On this visit the monitor will verify that the site has all the necessary documents for archiving, that all biological samples have been sent for analysis, that all the drug under study (used and unused) has been recovered and sent to the sponsor, and that all unused material has been recovered.

Details on monitoring are set out in the relevant plan

9.2 Audit and quality control

To ensure compliance with GCPs and all applicable regulatory requirements, Laboratorios Sophia, S.A. de C.V. may conduct quality assurance audits. Regulatory agencies could also conduct a regulatory inspection of this study.

Details about the audit process are set out separately in an Audit Plan.

9.2.1 Pre-study audit

Study sites included in the study will be patient for a pre-site site feasibility visit, where they will be verified to meet the minimum requirements indicated by the sponsor.

9.2.2 Auditing during the conduct of the study

They may take place at any time before, during, or after the conclusion of the study. If any audit or inspection is conducted, the investigator and the institution shall agree to allow the auditor/inspector direct access to all relevant documents and shall allocate their time and that of their staff to the auditor/inspector to discuss the findings and any pertinent problems. If the audit has not been scheduled by the sponsor, the facility must notify Laboratorios Sophia, S.A. de C.V. immediately.

10. Statistical analysis

10.1 Data analysis

10.1.1 Statistical Analysis

The statistical analysis will be carried out by personnel of Laboratorios Sophia, S.A. de C.V. The SPSS statistical package version 19.0 for Windows (IBM Corporation, Armonk, NY, USA) will be used. The coding will be done using consecutive numbers. The data will be collected and sorted in an Excel spreadsheet (Microsoft® Office). The data will then be exported to the SPSS package platform. The variables will be categorized according to their nature. See point 7.4.4 Definition of variables, methods and scales to be used for their measurement.

10.1.2 Data Interpretation

The Kolmogorov-Smirnov and Shapiro Wilk tests will be performed, as applicable, to determine if the distribution of the data is normal in the results obtained in each study group [56].

The results of the continuous quantitative variables will be presented in measures of central tendency: mean, standard deviation, standard error and/or ranges.

- Intra-group analysis: For equal variances, Tukey's POST-HOC test will be used, otherwise the Dunnett statistic will be used. One-way analysis of variance (one-way ANOVA) will be used when applicable.
- Intergroup analysis: Differences between groups will be analyzed using the Repeated Measures Analysis of Variance (ANOVA) test or the Student's t-statistic when applicable.

A non-inferiority margin (δ) of 10% will be used for the primary efficacy endpoint, based on the primary endpoint of the study. The level of difference to consider significance will be an alpha (α) of 0.05 or less.

The result of the nominal and ordinal qualitative variables will be presented in frequencies, proportions and/or percentages.

The statistical analysis to identify significant differences in the qualitative variables will be carried out by creating 2x2 contingency tables and will be carried out as follows:

- Intra-group difference: McNemar test. This is applied to 2x2 contingency tables with a dichotomous feature, with pairs of paired subjects, to determine if the marginal frequencies of row and column are equal (marginal homogeneity) [7].

- Difference between groups: Pearson's X² (Chi-square) test or Fisher's exact test at expected values less than 5.

The level of difference to consider significance will be an alpha (α) of 0.05 or less.

For the reporting of adverse events, all subjects who were randomly assigned to an intervention group after baseline (intention-to-treat population, ITT) will be considered.

The final report of the results will be shown in tables or graphs, as appropriate.

Variable Type	Variable	A1	B1	B2	C1	D1	D2	D3	D4	E1	E2
Background											
A1	Demographic	DT									
Basal											
B1	Medical History/Selection Criteria	DT									
B2	Comprehensive ophthalmological evaluation	DT				TB	T	T	T	TB	TB
Efficiency											
C1	OSDI	DB			B					TB	
Secondary efficacy outcome											
D1	TRLNI				DB	B				TB	
D2	Corneal and conjunctival stains (TVL and TF)		DT	DT			TB			TB	
D3	Conjunctival Hyperemia		DT	DT		TB				TB	
D4	Chemosis		DT	DT		TB				TB	
Safety											
E1	Incidence of AD				TB	TB	TB	TB	TB	TM	
E2	MAVC		DB							TM	B

D, Descriptive Statistics; T, 2x2 contingency table; B, Bivariate Analysis; M, Multivariate Analysis.

Table 3. Triangulation of concepts

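### For OSDI, TRLNI and BCVA, section 10.1.2 tests within-arm change with independent-sample methods and names no paired method

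*Combined protocol and SAP*

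**What the plan says.** Section 10.1.2 has two bullets for quantitative variables. The within-arm bullet begins "Intra-group analysis: For equal variances" and names Tukey's post-hoc test for that case, "otherwise the Dunnett statistic will be used"; it then adds "One-way analysis of variance (one-way ANOVA) will be used when applicable". The between-arm bullet reads "Intergroup analysis: Differences between groups will be analyzed using the Repeated Measures Analysis of Variance (ANOVA) test or the Student's t-statistic when applicable". No paired t-test, and no repeated-measures method, is listed for within-arm change.

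For qualitative variables the same section gives "Intra-group difference: McNemar test", which it explains as a test for paired data, and "Difference between groups: Pearson's X² (Chi-square) test or Fisher's exact test at expected values less than 5".

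Two other places bear on the point:

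- The synopsis (Statistical methodology) says only that ANOVA, of unstated type, serves for differences between groups.
- The variable table in section 7.4.4 lists both repeated-measures and one-way ANOVA for OSDI, TRLNI and BCVA. The one-way entry carries an asterisk that the text does not explain.

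By the schedule in section 1.3 and the visit descriptions in section 7.5.1, each of these three variables is measured before treatment (screening or baseline visit), at visit 1 and at the final visit.

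**The concern.** One-way ANOVA and the Tukey and Dunnett procedures that follow it treat the sets of values being compared as coming from different patients. Within an arm, the sets are visits and the patients are the same. An analyst who follows the bullet would enter visit as the factor and leave the variation between patients in the error term. A paired analysis removes that variation.

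At stake are the within-arm p-values for OSDI, TRLNI and BCVA. BCVA change is a safety variable (section 7.4.3), so a test with too little power could miss a real shift in mean acuity within an arm.

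**Working it through.** The plan states no figure that depends on this choice, so there is nothing of its own to reproduce. The check has two parts.

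**Reading the sections side by side**

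- In section 10.1.2 the qualitative bullets use the intra-group label for paired change (McNemar) and the between-group label for comparisons of arms (chi-square or Fisher). The same labels on the quantitative bullets should mean the same things. On that reading, one-way ANOVA with Tukey or Dunnett is assigned to paired data.
- The synopsis does not correct this, because it does not mention within-arm change.
- The table in section 7.4.4 does not clearly correct it either. For OSDI, TRLNI and BCVA, one-way ANOVA has the same asterisk as McNemar, which suggests the same assignment. For chemosis and adverse events, one-way ANOVA appears without an asterisk beside chi-square. With the asterisk unexplained, the table settles nothing.

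**Size of the effect**

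Inputs: alpha 0.05 (section 10.1.2; sidedness is not stated, two-sided assumed); 50 patients per arm before the allowance for losses (section 10.2.2); one value per patient per visit. The documents give no within-patient correlation r, so 0.3, 0.5 and 0.7 are assumed.

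For a change between two visits with common variance s² and n patients:

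- correct paired SE = sqrt(2s²(1-r)/n)
- independent-samples SE = sqrt(2s²/n)
- ratio = 1/sqrt(1-r), which does not depend on n

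True type I error of the nominal 0.05 test = 2 × (1 - Φ(1.96 × ratio)). Power where the paired test has 80% = Φ((1.96 + 0.8416)/ratio - 1.96).

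| Assumed r | SE ratio | True alpha | Power (paired 80%) |
|---|---|---|---|
| 0.3 | 1/sqrt(0.7) = 1.20 | 0.019 | 65% |
| 0.5 | 1/sqrt(0.5) = 1.41 | 0.006 | 51% |
| 0.7 | 1/sqrt(0.3) = 1.83 | 0.0004 | 34% |

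The formula covers two visits and the plan has three. A simulation therefore used three visits, n = 50, equal correlation between visits, no true change and 20,000 runs. One-way ANOVA rejected at rates of 0.016, 0.003 and below 0.001 for r = 0.3, 0.5 and 0.7. Repeated-measures ANOVA rejected at 0.052, 0.049 and 0.048. The direction is the same: with positive correlation the method as written is too conservative, and the paired method holds its level.

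**The case against.** **It may be a drafting slip.** Exchange the two labels and the quantitative bullets become conventional, and the phrase about applicability leaves some discretion. That is a fair guess at the intent. But the current text names no paired method for within-arm change, and neither the synopsis nor the table supplies one clearly.

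**The within-arm tests decide little.** This stands. Every objective in sections 3.1 and 3.2 compares arms, and no hypothesis rests on within-arm change. Section 10.1.2 plans no within-arm confidence intervals, so the effect falls on p-values. For BCVA, section 7.4.4.3 already treats a loss of more than two Snellen lines in a patient as an adverse event; what loses power is the test of mean change.

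Three stronger readings are tempting, and the documents do not support them:

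- *A reader might infer that the between-arm tests are also wrong.* Repeated-measures ANOVA with a treatment factor and a treatment-by-visit term can compare arms, and Student's t can compare Humylub with each comparator. This part is under-specified: no factors, deciding visit or contrasts are given. A treatment main effect averaged over all three visits would dilute a final-visit difference. If a difference D appeared only at the final visit, the average would be (0 + 0 + D)/3 = D/3.
- *A reader might infer that Dunnett is an invalid fallback for unequal variances.* The text says only "otherwise the Dunnett statistic will be used". Several procedures carry that name, and Dunnett's T3 and C are made for unequal variances. Set against Tukey for equal variances, that is the natural reading. The variant should be named, but none of these procedures deals with pairing.
- *A reader might infer a risk of false positive results.* With positive correlation the error runs the other way.

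**Conclusion.** The point holds for the quantitative variables OSDI, TRLNI and BCVA. Section 10.1.2 assigns independent-sample methods to within-arm change and names no paired alternative. For a two-visit change the standard error is 1.20 to 1.83 times too large over assumed correlations of 0.3 to 0.7, and a paired power of 80% falls to between 65% and 34%.

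These figures assume equal variances at the two visits and positive correlation. They illustrate the size and are not estimates for this trial. Unequal variances would make the ratio somewhat smaller at the same r.

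The categorical tests are correctly assigned. The error does not by itself affect the non-inferiority conclusion. It should be corrected because it is a stated rule that gives wrong within-arm p-values, one set of them for a safety variable.

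**What to change.** In section 10.1.2:

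1. Assign within-arm change in OSDI, TRLNI and BCVA to a paired t-test, or to a repeated-measures model over baseline, visit 1 and final visit.
2. For between-arm differences, state that the repeated-measures model includes treatment and treatment-by-visit terms. Name two final-visit contrasts: Humylub minus Hyabak and Humylub minus Lagricel.
3. Where a post-hoc procedure for unequal variances is kept, say which Dunnett variant is meant.
4. Align the synopsis, the table in section 7.4.4 (including the meaning of the asterisk) and section 10.1.2.

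These contrasts compare mean values. How non-inferiority is tested on the responder proportion in sections 3.3 and 10.2.2 is a separate matter that this change does not settle.

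The cost is plan wording only: no new data, visits or patients.

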7.4.4 Definition of variables, methods and scales to be used for the measurement

Variable	Conceptual Definition	Operational Definition	Measurement Type	Normal value	Statistical test
OSDI Score	OSDI is a questionnaire designed to establish a severity and Classification of dry eye according to its symptoms.	The evaluator will apply the questionnaire to the subject and allow the subject to answer it calmly without any pressure and/or coercion. See annex 16.1 OSDI .	Continuous quantitative	Score: OSDI= $\frac{\sum \text{score}}{25}$ n answers answered	
 • ANOVA of repeated measures. • One-way ANOVA*
TRLNI	Measurement of tear rupture time using non-invasive methods based on the observation of the film's mirror reflection in a grating design or in the placid discs of the corneal topographers and their analysis using specialized software.	The TRLNI will be measured by means of the Oculus Keratograph 5M.	Discrete quantitative	>10s	
 • ANOVA of repeated measures. • One-way ANOVA*
Corneal and conjunctival staining with lysmine green	Detection of epithelial defects in the conjunctiva and cornea.	Direct observation with slit lamp, graduation on Oxford scale. See annex 16.2 Oxford scale .	Ordinal Qualitative	Degrees: The stain is presented in a series of panels (A-E). The points Stains range from 0-5 for each panel and from 0-15 for the exposed toral area of the conjunctiva and cornea.	
 • χ^2 (Chi-square) of Pearson or Fisher's Exacta • McNemar Test*

Corneal and conjunctival staining with fluorescein	
Detection of epithelial defects in the conjunctiva and cornea.
	
Direct observation with slit lamp, graduation on Oxford scale. See annex 16.2 Scale of Oxford.
	
Ordinal Qualitative
	
Degrees: The stain is presented in a series of panels (A-E). The points Stains range from 0-5 for each panel and from 0-15 for the exposed toral area of the conjunctiva and cornea.
	
 • χ^2 (Chi-square) of Pearson or Fisher's Exacta • McNemar Test*

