Conjunctival Hyperemia Changes	
It is defined as the simplest reaction of the conjunctiva to a stimulus, a red appearance is seen secondary to vasodilation of the conjunctival vessels of variable intensity.
	
Direct observation. Classification by Efron scale. See annex 16.3 Efron's scale.
	
Ordinal qualitative
	
Degrees: 0= Normal, 1= Very mild, 2= mild, 3= Moderate and 4= Severe
	
 • χ^2 (Chi-square) of Pearson or Fisher's Exacta • McNemar Test*
Incidence of chemosis	
It is defined as conjunctival edema resulting from an inflammatory reaction. It is classified as present or absent.
	
The evaluator will use a narrow beam of light at 60° and measure whether the conjunctiva separates by $\geq 1/3$ of the total palpebral aperture or whether it exceeds the gray line
	
Ordinal qualitative
	
Present/absent
	
 • One-way ANOVA • Pearson's χ^2 (Chi-square) or Fisher's Exact test
Incidence of AEs	
Any adverse medical event that occurs in a patient or clinical research subject who has been administered a pharmaceutical product and that does not
	
The AEs manifested during the conduct of the study will be collected using the FRCE.
	
Continuous quantitative Categorical qualitative
	
Frequency Subjects presenting EA/total number of subjects exposed. Intensity
 • Mild • Moderate • Severe Causality
	
One-way ANOVA Pearson's χ^2 (Chi-square) or Fisher's Exact test

- Probable
- Possible
- Unlikely

Changes BCVA	Spatial VA is the ability to distinguish separate elements of an object and identify them. It is quantified as the minimum angle of separation (located at the nodal point of the eye) between two objects that allows them to be perceived as separate objects	Snellen chart	Discrete quantitative	Fraction 0.6 to 2.0	ANOVA for repeated measures. • One-way ANOVA*
--------------	-----------------------------------------------------------------------------------------------------------------------------------------------------------------------------------------------------------------------------------------------------------------	---------------	-----------------------	-------------------------------	----------------------------------------------------------------

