10.2 Sample Size Calculation

10.2.1 N Calculated

Number of planned patients: 60 evaluable patients (both eyes) per arm

Total N = 180 patients

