10.2.2 Justification for sample calculation

Sample size calculation was performed based on the results of the phase IV, multicenter, prospective, double-blind, randomized efficacy and safety clinical study of Humylub Ofteno® PF ophthalmic solution, versus Systane® Ultra and Systane® Ultra preservative free performed in subjects diagnosed with mild to moderate dry eye. The reduction in the mean score of the OSDI test was considered as the main efficacy variable, with a dosage of 1 drop QID. In this study, after one month of treatment, subjects assigned to Humylub Ofteno® PF had a decrease of -49.3% vs -41.3% for Systane Ultra and -48.3% for Systane Ultra PF, with respect to their initial mean values with no statistical differences between treatments ($p>0.05$) [57].

For the present protocol, it is expected that, after 3 days of treatment, 30% of subjects treated with Humylub Ofteno® PF will have a 35% decrease in OSDI score compared to their initial mean value.

The sample size was calculated using the equation for two proportions [58], considering a power of 80% (β), a significance level of 0.05 (α) and a margin of non-inferiority (δ) of 10% and based on the following working hypotheses:

$$H_0: P_A - P_B \leq \delta$$

$$H_1: P_A - P_B > \delta$$

Where, δ is the margin of non-inferiority and, the ratio between the sample size of the two groups is:

$$k = \frac{\eta A}{\eta B}$$

Equations

The calculation to estimate sample size and power was performed using an online tool and following the equations: [59]

$$n_A = kn_B \text{ y } n_B = \left(\frac{P_A(1 - P_A)}{k} + P_B(1 - P_B) \right) \left(\frac{z_{1-\alpha} + z_{1-\beta}}{p_A - p_B - \delta} \right)^2$$

$$1 - \beta = \Phi(z - z_{1-\alpha}) + \Phi(-z - z_{1-\alpha}) \text{ , } z = \frac{P_A - p_B - \delta}{\sqrt{\frac{P_A(1 - P_A)}{n_A} + \frac{P_B(1 - P_B)}{n_B}}}$$

$$k=nA/nB$$

Φ is the standard normal distribution function

Φ^{-1} is the standard normal quantile function

α is a Type I error,

β is the Type II error, which means that $1-\beta$ is the power, and

δ is the test margin.

According to the previous calculation, the result was 50 subjects, this calculation was increased by 20% considering possible losses (10 subjects). The total suggested sample size is 180 subjects (60 cases per arm), which will provide both eyes for the study.

11. Ethical considerations

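### No rule says how a patient's two eyes enter the between-group tests of acuity and staining; if entered as separate records, the nominal 5% error is exceeded, except for rare staining categories

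*Combined protocol and SAP*

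**What the plan says.** All references are to the combined protocol and SAP.

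- **Recording.** Section 7.4.4.3 takes acuity in the right and then the left eye. Section 7.4.4.5 has the fluorescein grade entered separately for each eye. Section 7.4.4.6 (lissamine green) repeats that recording sentence and still names fluorescein, apparently by carry-over; the natural reading is that lissamine grades are also per eye.
- **Eyes in the study.** Section 10.2.1: "Number of planned patients: 60 evaluable patients (both eyes) per arm". Section 10.2.2: "The total suggested sample size is 180 subjects (60 cases per arm), which will provide both eyes for the study". Section 10.1.3 includes both eyes of every exposed patient in the safety assessment, and acuity is a safety variable (7.4.3).
- **Between-group tests, quantitative outcomes.** Section 10.1.2: "Differences between groups will be analyzed using the Repeated Measures Analysis of Variance (ANOVA) test or the Student's t-statistic when applicable". The acuity row of the 7.4.4 table also lists "ANOVA for repeated measures".
- **Between-group tests, qualitative outcomes.** These are to be "carried out by creating 2x2 contingency tables", using chi-square, or "Fisher's exact test at expected values less than 5". The staining rows of 7.4.4 agree: "Chi-square) of Pearson or Fisher's Exacta".
- **Objectives.** Section 3.2 words the secondary objectives, including staining and acuity, as non-inferiority. Section 10.1.2 gives a margin for the primary endpoint only.

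No section names a study eye, a mean-of-eyes or worse-eye rule, eye as a within-subject factor, or a method clustered on patient.

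**The concern.** Two eyes of one patient receive the same product and share the same tear-film disease, so their values are expected to correlate. Student's t, chi-square and Fisher's test assume independent records. Repeated-measures ANOVA handles repeated visits, but handles paired eyes only if eye is declared a within-subject factor.

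With 60 patients per arm there are 60 x 2 = 120 eye records per arm. Entering them as 120 independent units makes standard errors too small. Tests of difference between products then reject too often, and any confidence interval used for a secondary non-inferiority objective is too narrow.

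Leaving the unit open also lets it be chosen after the data are seen. The trial is open-label (4.1) and is analysed by sponsor staff (10.1.1).

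**Working it through.** **Inputs from the documents.** Alpha 0.05 (10.1.2; two-sided assumed for tests of difference). Three arms of 60 patients with two eyes each (10.2). Three assessments of acuity and staining: screening, visit 1 and final (patient schedule, 1.3). Chi-square, switching to Fisher when an expected count is below 5 (10.1.2).

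**Input not in the documents.** The between-eye correlation, rho, of the quantity tested. That quantity may be a level or a change; the outcomes are defined as changes (7.4.2, 7.4.3). Assumed range 0.3-0.9, with 0.1-0.2 shown as a low case.

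**Step 1. Variance.** With n patients and two eyes each, the variance of an arm mean is sigma²(1 + rho)/(2n). Treating eyes as independent gives sigma²/(2n). The ratio is 1 + rho, so the correct standard error is sqrt(1 + rho) times the pooled one.

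**Step 2. True error of a nominal 5% test, eyes as separate records (large-sample).**
- Two-arm t: 2 x [1 - Phi(1.96/sqrt(1 + rho))].
- Three-arm group effect: P(chi-square on 2 df > 5.991/(1 + rho)).
- Three-arm group-by-visit effect, three visits, (3-1) x (3-1) = 4 df: P(chi-square on 4 df > 9.488/(1 + rho)), with sphericity assumed and rho taken for the visit-to-visit changes.

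At rho = 0 all three return the plan's 5%.

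| rho | SE ratio | two-arm t | group effect | group-by-visit |
|---|---|---|---|---|
| 0.1 | 1.05 | 6.2% | 6.6% | 7.1% |
| 0.2 | 1.10 | 7.4% | 8.2% | 9.5% |
| 0.3 | 1.14 | 8.6% | 10.0% | 12.1% |
| 0.5 | 1.22 | 11.0% | 13.6% | 17.6% |
| 0.7 | 1.30 | 13.3% | 17.2% | 23.3% |
| 0.9 | 1.38 | 15.5% | 20.7% | 28.8% |

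Worked line, rho = 0.5: 1.96/sqrt(1.5) = 1.600, two-sided tail 11.0%. 5.991/1.5 = 3.994, tail exp(-1.997) = 13.6%. 9.488/1.5 = 6.325, tail exp(-3.163) x (1 + 3.163) = 17.6%.

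**Step 3. Simulation check.** Repeated-measures ANOVA with each eye as a subject, three visits, no true difference, 50 or 60 patients per arm:
- Group effect about 8%, 13-14% and 20% at rho 0.2, 0.5 and 0.8.
- Group-by-visit effect about 9-10%, 17-18% and 26-27% at the same values.

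In a separate simulation with 60 per arm, the pooled two-arm t gave 8.8%, 10.7%, 13.6% and 15.7% at rho 0.3, 0.5, 0.7 and 0.9.

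**Step 4. Staining 2x2 rule.** Two arms, 120 pooled eyes per arm, chi-square/Fisher switch, simulated:

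| eyes in category | rho 0.3 | rho 0.5 | rho 0.7 | rho 0.9 |
|---|---|---|---|---|
| 1% | 0.4% | 0.7% | 1.2% | 1.8% |
| 2% | 2.0% | 2.8% | 4.1% | 6.1% |
| 5% | 7.6% | 9.4% | 11.5% | 14.2% |
| 10% | 8.9% | 11.5% | 13.6% | 15.9% |
| 50% | 8.0% | 10.6% | 12.4% | 14.8% |

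Exact enumeration at 60 patients per arm agrees. The error first passes 5% at a prevalence of about 4% (rho 0.3), 3% (0.5), 2.5% (0.7) and 2% (0.8 and 0.9). Below that, the conservatism of Fisher's test offsets the inflation. Acuity, tested as quantitative, has no such offset.

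**Step 5. With the correlation respected.** One mean per patient gives 4.7-5.3% for the t test and one-way ANOVA at every rho from 0 to 0.9. Repeated-measures ANOVA with eye as a within-subject factor gives 4.9-5.3% (group) and 4.6-5.1% (group-by-visit).

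**The case against.** The strongest reply is that the plan never says eyes will be pooled. Its N is 180 patients, its replacement rule (10.1.4) counts patients, and its description of McNemar speaks of paired subjects. The mentions of both eyes can be read as saying which data are collected, not what the unit of analysis is. This stands: the error rates above belong to one possible analysis, and a reader who infers that the plan commits to 120 independent eyes per arm goes beyond the text. But counting patients does not turn two acuities or two grades into one value. Mean, worse eye, right eye and pooling all remain open.

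A second reply is that repeated-measures ANOVA, already named, can be valid. That is so with eye as a within-subject factor, but the plan does not say this, and staining goes to 2x2 tests in any case.

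Third, neither rho nor any staining prevalence is in the documents, and no cut-point is given for reducing the grades to 2x2 tables. This also stands. The sizes are conditional, and at rho 0.1-0.2 the excess is only about 1 to 5 percentage points.

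Fourth, only secondary and safety measures are touched. That is correct and sets the priority.

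**Conclusion.** The gap is real: outcomes recorded per eye are assigned tests with no provision for two eyes per patient. If eyes are entered as separate records and rho is 0.3-0.9, true error is about 9-16% for a two-arm t test, 10-21% for the three-arm group effect and 12-29% for group-by-visit. At rho 0.1-0.2 these are about 6-7%, 7-8% and 7-10%. The staining tests reach about 8-16% when 5-50% of eyes are in the category. They stay at or below 5% when it is rare (about 2% or less, except at the highest correlations).

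For non-inferiority the direction depends on how it is judged, which the plan does not say for secondary outcomes. With confidence intervals, pooling makes the claim too easy, since correct standard errors are 1.14-1.38 times the pooled ones at rho 0.3-0.9. If absence of a significant difference were the criterion, pooling would make the claim harder to reach.

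A reader might infer that the main result is compromised. The documents do not support that. OSDI yields one score per patient, the sample size is in patients, and adverse-event incidence is defined as "Subjects presenting EA/total number of subjects exposed". Nor can break-up time or hyperemia be counted as affected, because the plan does not state whether they are analysed per eye. Priority: low to moderate.

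**What to change.** In section 10.1.2 and the 7.4.4 table:

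1. State that the patient is the unit of inference for every comparison.
2. Analyse acuity as the mean of both eyes per patient at each visit. Equivalently, keep both eyes with eye as a within-subject factor in the repeated-measures ANOVA already named.
3. Analyse staining grades with both eyes in a GEE clustered on patient, replacing chi-square or Fisher on pooled eyes.
4. State whether break-up time, hyperemia and chemosis are recorded per eye, and apply the same clustered method to any that are.

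**Cost.** An amendment with committee review and regulatory authorization (11.2). No new data, visits or patients are needed. Standard errors will be about 14-38% larger than pooled ones at rho 0.3-0.9, which is their correct size.
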